#### 4.2 Exclusion Criteria

- HIV positive (self-report or laboratory confirmed)
- Chronic Hepatitis B or no verification of hepatitis B vaccination
- Currently enrolled in any HIV prevention trial (biomedical)
- Currently taking oral PrEP based on self-report
- Creatinine clearance <60 ml/min based on the Cockcroft-Gault equation
- Symptoms of acute HIV infection within the prior 30 days
- Contraindications to taking oral PrEP
- Personal diagnosis or family history of hemophilia
- Health insurance with Kaiser Permanente (unable to prescribe PrEP through the study)
- Investigator discretion to exclude anyone whose best interest is not to participate
- Evidence of fraudulent participation, such as duplicate IP address, multiple screening attempts, duplicate emails, etc

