#### 5.4.2 PrEP Initiation/Continuation

If laboratory, clinical and behavioral survey results do not show contraindications to PrEP initiation/continuation, the study clinician will initiate or renew the PrEP prescription. Eligible participants will be initiated with a 3-month prescription for FTC/TDF or FTC/TAF by the site study clinician. Standard PrEP financial navigation services will be delivered by study staff trained in order to ensure uniformity of intervention provision. The navigation will use Gilead medication assistance and co-pay access programs, in addition to state-specific programs, to facilitate access to PrEP at low or no cost to participants. We will seek to make home delivery of PrEP prescriptions from pharmacies available. If a participant's insurance does not allow for the home delivery, participants will pick up PrEP from their preferred local pharmacy. Enrolled participants not on PrEP, due to discontinuation or never having initiated, will continue participation in the scheduled research assessments. With clinician guidance, such participants can choose to uptake PrEP at any point during the study.

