### 5.5 Laboratory Procedures

All study lab tests will be conducted at CLIA-certified laboratories using FDA-approved tests. Participants will self-collect whole blood in microtubes from finger prick for creatinine and syphilis (using antibody test with reflexive RPR) tests. Whole blood collected on dried blood spot (DBS) cards will be used for HIV testing. Pharyngeal swabs, rectal swabs and a urine sample will be collected for gonorrhea and chlamydia testing. Hepatitis B surface antigen will be tested either through Quest/LabCorp, local health department, or self-collect. Participants may be referred to local testing services, if needed. The Alabama Department of Public Health, Georgia Department of Public Health, Mississippi State Department of Health, and the North Carolina Department of Health and Human Services will be notified of confirmed positive results in accordance with state public health reporting laws, a procedure that will be explained to participants at consent.

*Baseline testing:* All participants will be tested for HIV, syphilis, creatinine, gonorrhea, chlamydia, and Hepatitis B.

*Follow-up testing:* Intervention participants will be tested for HIV, syphilis, gonorrhea, and chlamydia quarterly. Creatinine will be tested at months 3 and 9. All participants are scheduled to return DBS cards for TFV-DP testing at months 6 and 12.

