#### 5.5.4 Dried Blood Spots

Participants will be informed of expectations regarding specimen collection at baseline. DBS cards will be sent to both intervention and control participants for primary outcome assessment at 6 months and 12 months. Spots will be collected on a filter paper card and dried for  $\geq 4$  hours prior to mailing. Once returned to the lab, the primary outcome assessment DBS specimens will be stored in a laboratory freezer at  $-20^{\circ}\text{C}$  until they are batch tested for TFV-DP levels at the UNC [name] Lab. The [name] Laboratory will also measure emtricitabine-triphosphate (FTC-TP) from the DBS cards for secondary analyses.

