### 8.0 PARTICIPANT MANAGEMENT

#### 8.1 Tracking Participants / Follow-up

All participants will be followed prospectively for 12 months after assignment to the intervention or control conditions. Research assessments, completed at the participant's home, will be identical for intervention and control participants: surveys at 3, 6, 9, and 12 months, and DBS specimen collection and mailing at 6 and 12 months. All participants will be reminded of their upcoming assessments through the study app. All participants will be followed up for study retention regardless of whether they are actively taking PrEP and/or engaged in PrEP care.

Intervention participants will have a 1-month telemedicine consult with the ePrEP site study staff or clinician, providing an open forum to answer questions/concerns, assess side effects, adherence, behavioral risk, symptoms of acute HIV infection or STD, and provide appropriate clinical management. The intervention arm will have home test lab assessments and telemedicine consultations at 3, 6, 9 and 12 months with their ePrEP site study clinician. Participants assigned to the intervention will receive automatic reminders for scheduled ePrEP site study clinician telemedicine consultations.

Control participants will complete surveys at 3, 6, 9, and 12 months, and home DBS specimen collection and mailing at 6 and 12 months. Control participants will be sent electronic reminders to complete their research assessments. Follow-up calls may also be used for participants who need further reminding and additional follow-up.

All study virtual visits have a set window period for the participant to complete. If a participant misses a virtual visit or scheduled follow-up assessment, they will be allowed to continue in the study for the following virtual visits. They will remain on a 12-month study timeline.

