## 10.3 Statistical Analysis Plan

10.3.1 Aim 1: Analyses of primary outcome that control for potential residual confounding, and analyses of secondary outcomes including initiation of and retention in PrEP care.

Logistic regression and log-linear models will be used to estimate the association between intervention arm and the primary study outcome, TFV-DP level. If prognostic factors associated with the outcome remain insufficiently balanced through stratified randomization, we may adjust for these factors in our models. Potential confounding factors that may be included are medication self-efficacy and motivation to take PrEP. Per protocol assessments that account for potential

changes in intervention as delivered will be conducted. For instance, this would account for participants assigned to the intervention condition opting to instead receive standard of care PrEP from a non-study clinician. A number of secondary analyses will be conducted using regression models. Intervention impact on the secondary outcomes of PrEP initiation and PrEP persistence will be determined using analogous regression models. Another secondary analysis will be to model  $\log_{10}$  (TFV-DP levels) as the outcome variable. An additional secondary analysis will account for changes in PrEP eligibility over time, per CDC guidelines. This has the potential to detect significant smaller “sub-clinical” differences in adherence between the intervention and control study arms. Similarly, an analysis with FTC-TP will allow for a more sensitive and sub-clinical assessment of PrEP use. Other specific and aggregate measures of safety including: renal function, HIV incidence, and incident bacterial STI will be assessed.

**10.3.2 Aim 2: Exploratory analyses of intervention effectiveness across subgroups, and analysis of potential mediators of initiation or persistence in PrEP care across both study arms, such as self-efficacy and urbanicity.**

Heterogeneity of the intervention effects across subgroups will be explored, including that of stratification (race), and socioeconomic indicators. Understanding variables associated with success or failure in home care for PrEP will inform future research, and potentially guide clinician recommendations or policy regarding bringing PrEP to scale. For participants who seroconvert during the study, levels of TFV-DP, PrEP persistence, and other clinically-relevant study data will be analyzed.

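### Does the secondary log10(TFV-DP) model need a written rule for undetectable results?

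*Combined protocol and SAP*

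**What the plan says.** Section 10.3.1 lists, among several secondary analyses, a model of log10 "TFV-DP levels) as the outcome variable". After an intervening sentence on PrEP eligibility it refers to smaller "differences in adherence between the intervention and control study arms", and then adds that "an analysis with FTC-TP will allow for a more sensitive and sub-clinical assessment of PrEP use". It states no limit of detection or quantification and no rule for results below one. The laboratory sections cover collection, storage and batch testing. The only TFV-DP threshold in the document is the protection cut-point of 700 fmol/punch in Section 10.1.2.

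The design makes undetectable results likely:

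- Section 4.2 excludes anyone "Currently taking oral PrEP based on self-report", so participants start without reported drug exposure.
- Section 5.4.2: "Enrolled participants not on PrEP, due to discontinuation or never having initiated, will continue participation in the scheduled research assessments".
- Section 8.1: "All participants will be followed up for study retention regardless of whether they are actively taking PrEP and/or engaged in PrEP care".
- Section 5.5: "All participants are scheduled to return DBS cards for TFV-DP testing at months 6 and 12". Section 5.5.4 repeats this by arm: "DBS cards will be sent to both intervention and control participants for primary outcome assessment at 6 months and 12 months".

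Section 10.5 deals with missing data. It accepts complete-case analysis when few cases are missing and turns away from it when bias would follow. It leaves the form of any imputation to depend on the data.

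**The concern.** An undetectable result is observed, not missing, so Section 10.5 does not strictly cover it. Because log10 of zero is undefined, the model cannot be fitted to every returned card until someone decides how these results enter. The candidates are to drop them, substitute a constant, treat them as censored, rank them lowest, or split the analysis into any drug versus none and level among users.

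These choices do not answer the same question. Dropping compares users only, a group formed after randomisation, and can hide or reverse a difference in uptake. A very low constant makes the model mainly a test of any drug against none, while a constant near the limit gives more weight to level. If the rule is open, it could be chosen after the undetectable counts by arm are known. At stake are what this analysis can detect and the ratio it reports.

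**Working it through.** **1. The plan's own figure.** Section 10.2 gives 5% v 18% above the cut-point, two-sided 5%, 80% power and 20% attrition; Section 3.2 gives 120 per arm.

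- n per arm = [1.960 x sqrt(2 x 0.115 x 0.885) + 0.842 x sqrt(0.05 x 0.95 + 0.18 x 0.82)]^2 / 0.13^2 = (0.884 + 0.372)^2 / 0.0169 = 93.4, so 94.
- Allowing for attrition: 94 / 0.80 = 117.5, so 118, against 120 planned.
- With 120 x 0.80 = 96 evaluable per arm, power is 81.1%.

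The stated figure reproduces. It concerns the binary primary outcome; no figure is given for the log10 model.

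**2. Effect on the primary outcome.** The outcome is scored as above 700 or not. For any assay limit below 700, an undetectable result is scored as not above. The rule for the log10 model cannot change it.

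**3. Assumptions for the log10 model.** None of these is in the documents: limit 25 fmol/punch; low users log-uniform from 25 to 700; protected users uniform from 700 to 1,800; undetectable shares as given below. There are 96 per arm, with Welch tests on log10 for substitution and dropping. The two-part test adds a likelihood-ratio test of the measurable share to the Welch test among measurable samples (2 df). Mean log10 is (1.398 + 2.845) / 2 = 2.122 for low users and 3.082 for protected users.

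**4. The case tied to the plan's effect.** Control: 85% undetectable, 10% low, 5% above 700. Intervention: 65%, 17%, 18%. With undetectable results set to c, the difference in mean log10 is

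(0.65 - 0.85) x log10 c + 0.07 x 2.122 + 0.13 x 3.082 = 0.549 - 0.20 x log10 c.

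- c = 25: 0.270, ratio 1.9
- c = 12.5: 0.330, ratio 2.1
- c = 1: 0.549, ratio 3.5

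Power by simulation is about 91-93% for all three constants, 92-93% for ranks and 87-88% for the two-part test. Lowering c widens the difference and the spread together, so the test barely moves while the ratio nearly doubles.

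**5. Cases where the rule does matter.** Here the share above 700 is set equal in both arms, at 5%.

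| Setting | c = 25 / 12.5 / 1 | Ranks | Two-part | Dropping |
|---|---|---|---|---|
| Uptake differs, 85% v 68% undetectable | 45 / 55 / 70% | 75% | 76% | 15% |
| Level differs, 60% undetectable in both, low users from 25 v 150 | 39 / 28 / 12% | 15% | 90% | 95% |

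In the first row the substitution difference is 0.17 x (2.122 - log10 c), giving ratios of 1.3, 1.5 and 2.3. Dropping reverses the sign: control (10 x 2.122 + 5 x 3.082) / 15 = 2.442, intervention (27 x 2.122 + 5 x 3.082) / 32 = 2.272, ratio 10^(-0.170) = 0.68.

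**6. Does one replacement rule dominate?** The two-part test leads clearly when only level among users differs by a wide margin. Elsewhere it does not:

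- 15% v 35% above 700 with 40% v 25% undetectable: 78%, against 82-86% for substitution and ranks.
- Second row of the table with a milder contrast (low users from 25 v 75): 42-46%.
- Second row of the table with 85% undetectable: 18-19%.

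**The case for a change.** The best argument for a change is that it would cost two or three sentences and no new data, and would remove a choice that could otherwise follow sight of the counts. The direction of the effect does not depend on one set of assumptions. With lognormal levels among users (median 800) and uptake set so that 5% v 18% exceed 700, dropping undetectable results gives about 5% power, while substitution gives 97-99%. With 30% uptake in both arms and a two-fold difference in level, dropping gives 58-99% and substitution 7-16%.

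Part of this stands. The rule is unwritten, dropping would be a poor choice, and a ratio from substitution means little without its constant. Power can also depend on the constant when the arms differ above 700: at 60% v 50% undetectable and 5% v 18% above 700, substitution ranges over about 50-65%.

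Three things limit it. The plan never says undetectable results will be dropped, and Section 10.5 already turns away from complete-case analysis where it would bias results. The widest contrasts need settings that the documents do not suggest, such as uptake rising from 15% to 32% with nobody added above 700. And the two-part test takes much of its advantage from the comparison among users, which is itself post-randomisation; a significant joint result has no direction and does not identify an adherence effect. The link between the sentence on smaller adherence differences and the log10 model is also an inference, since that sentence directly follows the one on PrEP eligibility.

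**Conclusion.** No change to the plan is called for. This is an unwritten detail of one secondary analysis that analysts have to settle in order to fit the model, and several sound options exist: ranks, a censored model, a two-part model, or substitution with the constant reported. Initiation and persistence, which carry the uptake question, are separate secondary outcomes in Section 10.3.1.

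In the case tied to the plan's 5% v 18%, the substituted constant leaves power at about 91-93% and moves the ratio from about 1.9 to 3.5. The two-part test would cost about 5 points there and gain heavily only where level among users differs strongly, so statisticians could reasonably differ over it. All figures for the log10 model rest on an assumed limit, assumed undetectable shares and assumed level distributions; only the 96 per arm and the 5/18% and 15/35% shares come from the plan. The assay limit may be recorded in laboratory documents outside this one. The same reasoning applies to FTC-TP if it is modelled as a continuous level.

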## 3.0 STUDY DESIGN

PrEP-naïve MSM will be recruited into the study, with a focus on Black and Latino MSM, targeted to make up half of all participants. A screening will be conducted online and involve a screening consent and questions to determine initial eligibility. This will be followed by a full consent (if eligible), a baseline survey, and the return of self-collected specimens for testing to determine clinical PrEP eligibility. Those eligible for the study will be enrolled into the trial and randomized to either intervention (ePrEP) or control (standard of care). Participants assigned to the ePrEP intervention (n=120) will have a baseline teleconsultation with a site study clinician who will be responsible for prescribing PrEP as indicated.[10] Intervention participants will be offered telemedicine consultations at 1, 3, 6, 9 and 12 months, and will complete quarterly home specimen collection for laboratory tests recommended by CDC at each time period. The study

virtual visits consist of surveys, specimen collection, and telemedicine consultation. Those assigned to the control condition (n=120) will be referred to a publicly available website that geolocates the nearest PrEP provider, [www.PrEPLocator.org](http://www.PrEPLocator.org). Both conditions will have identical TFV-DP kit collection for primary outcome assessments (6 and 12 months) and app-based surveys for secondary outcomes assessments across all study periods (baseline, 3, 6, 9, and 12 months).

The three study sites will be staffed by clinicians who will conduct telemedicine consultations and supporting staff who will address participant care needs such as referrals for treatment. Study recruitment, retention communication, and tracking will be handled by staff at the Emory University site.

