##### Study App:

The study app, eP, serves as the primary participant-facing component of the intervention. The eP app, which will be downloaded on participants' phones, includes many features to facilitate remote care. Electronic messaging features provide a means for participants to communicate with their clinical care team through secure messages, or send documentation needed for PrEP navigation through secure photos. Surveys are hosted in the app, and used to populate key forms and answer key clinical questions such as medication adherence. Automated notifications of progress and appointment reminders are sent, seeking to facilitate engagement in care. A timeline-based view shows progress in care, and next steps such as upcoming virtual visits or home test kits to be completed. Telemedicine consultations with study clinicians will occur within the app through secure video, and scheduling of these consultations will be accomplished through a calendaring function. A preferences function will allow participants to alter their profile such as changing preferred pharmacy or home shipping address. Some of the app features, particularly messaging and survey functionalities, will also be used to incorporate components of interaction that are specific to research study participation. The app is hosted in a secure environment, compliant with all relevant security protocols, and will use password protected entry to enhance privacy. (Section 7.3.4)

The eP app has two versions: one for the intervention group and one for the control group. When participants first download the app, they will only be able to see the initial parts of the app needed for study initiation: baseline survey modules and home test kit tracking. Once the participant is randomized, their version of the app will open up to show them the timeline of the study visits information based on the group they are assigned. The intervention group will be able to see and use all components of the eP app. The control group will only be able to see the parts of the app that are applicable to research: surveys, tracking home test specimens (the mail-in DBS card for TFV-DP), and messaging functionality for communication with study staff.

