#### 5.5.2 STI Testing

All participants will be tested for syphilis and pharyngeal, urethral, and rectal gonorrhea and chlamydia at Baseline. Intervention participants will be tested for syphilis gonorrhea, and chlamydia (pharyngeal, urethral and rectal) at quarterly follow-up virtual visits. Reflexive RPR titer will be conducted if the syphilis antibody test is reactive. Hepatitis B surface antigen will be tested to determine chronic hepatitis B status at Baseline.

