#### 6.1.3 On-Study measures

- 1-Month CRF: Intervention participants will have a telemedicine consultation with study staff or clinician to assess experiences one month after initiating PrEP. CRF will record adherence and side effects.
- Surveys for participants in both arms at months 3, 6, 9 and 12: categories include sexual behavior, PrEP cascade, and the validated system usability scale (SUS).

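### Does intervention-only follow-up testing bias the planned assessment of HIV incidence, bacterial STI and renal function?

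*Combined protocol and SAP*

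**What the plan says.** Section 10.3.1 closes its list of secondary analyses by saying that "renal function, HIV incidence, and incident bacterial STI will be assessed". It does not say whether this is descriptive, comparative or pooled.

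The testing schedule differs by arm after baseline:

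- Section 5.5: "Intervention participants will be tested for HIV, syphilis, gonorrhea, and chlamydia quarterly".
- Section 5.5.2: "Intervention participants will be tested for syphilis gonorrhea, and chlamydia (pharyngeal, urethral and rectal) at quarterly follow-up virtual visits".
- Section 8.1, intervention: "The intervention arm will have home test lab assessments and telemedicine consultations at 3, 6, 9 and 12 months".
- Section 8.1, control: "Control participants will complete surveys at 3, 6, 9, and 12 months, and home DBS specimen collection and mailing at 6 and 12 months".
- Section 5.4.1, on the control version of the app: it shows the surveys, messaging and "tracking home test specimens (the mail-in DBS card for TFV-DP").
- Section 3.0, on intervention participants: they "will complete quarterly home specimen collection for laboratory tests recommended by CDC at each time period".

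Section 11.3.2 lists HIV and STI testing as a benefit for everyone only at study initiation. Two items name no arm: quarterly HIV testing in 6.2.2, and creatinine at months 3 and 9 in 5.5 and 5.5.3.

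Control events can still reach the study. Section 6.1.3 has "Surveys for participants in both arms at months 3, 6, 9 and 12: categories include sexual behavior, PrEP cascade", and 8.4 makes a confirmed positive HIV test a possible reason for discontinuation, with withdrawal reasons recorded.

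**The concern.** Most of 10.3.1 is about comparing arms by regression, and it refers to a number of secondary regression analyses without listing them all. A reader could therefore expect HIV incidence and STI incidence to be tabulated by arm. One arm is screened every quarter; the other is seen through surveys and withdrawal records. With equal true incidence, the screened arm would show more infections, and that excess could be read as harm or as risk compensation caused by ePrEP. A pooled rate that counted untested controls as event-free would be too low.

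Section 9.0 also has the Safety Monitoring Committee follow seroconversion and kidney function without naming an arm, and 10.3.2 plans to analyse seroconverters from the whole trial. Section 10.5, on missing data, does not separate a missed test from one that was never scheduled.

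**Working it through.** **Inputs from the plan.** 120 per arm (3.2), 20% attrition in both arms and a two-sided 5% level (10.2.1). Evaluable per arm: 120 × 0.8 = 96.

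**The plan's own figure.** For 5% against 18% with 96 per arm, a pooled-variance two-proportion calculation gives 81.1% power. The required 94 per arm becomes 94/0.8 = 117.5, so 118 per arm and 236 in total, against 240 planned. The figure in 10.2.1 reproduces. It concerns TFV-DP only and does not depend on HIV, STI or creatinine testing.

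**Assumed inputs.** The documents give no HIV or STI incidence and no detection share. Take the same true 12-month risk r in both arms, and let dI and dC be the shares of events recorded in the intervention and control arms.

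- Apparent risk ratio = dI/dC. With dI = 1 and dC = 0.25, 0.50, 0.75: 4.0, 2.0, 1.33.
- Pooled understatement, if untested controls are counted as event-free, = 1 − (dI + dC)/2: 37.5%, 25%, 12.5%.
- Example, r = 0.20 and dC = 0.50: 96 × 0.20 = 19.2 recorded events against 96 × 0.10 = 9.6; pooled rate (0.20 + 0.10)/2 = 0.15.
- Intervention arm over its own tested participants: 19.2/96 = 0.20, the true risk. The understatement disappears.

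**If someone ran a test.** Rejection rates by exact binomial enumeration, 96 per arm, dI = 1, for dC = 25%/50%/75%:

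| Assumed risk | Pooled z test, absolute z > 1.96 | Fisher's exact, p < 0.05 |
|---|---|---|
| 20% | 91% / 50% / 15% | 43% at dC = 50% |
| 10% | 59% / 26% / 10% | 18% at dC = 50% |
| 5% | 30% / 13% / 6% | 15% / 6% / 3% |
| 2% | 8% / 5% / 4% | under 1% throughout |

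With full detection in both arms the z test rejects 5.1%, 5.2%, 4.3% and 3.8% of the time at these four risks. With dI = 0.8 and r = 0.20 the z-test figures fall to 73%, 24% and 5%.

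At STI-like risks the distortion would be material under either test. At HIV-like risks of 2% to 5%, expected recorded events are about 2 to 5 in the intervention arm and fewer in the control arm, and the answer depends largely on the test chosen.

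**Does the plan call for such a test?** Section 10.3.1 names regression models of intervention impact for PrEP initiation and persistence. For the three safety measures it says only that they will be assessed. Section 10.3.2 looks at drug levels and persistence among people who seroconvert, which is not an incidence comparison. In 9.0 the efficacy bounds of ±2.96 are tied to the primary outcome. In 10.4 infections averted are projected by a model, not counted by arm.

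**Renal function.** The detection model does not apply. A control without a creatinine test has a missing value, not a recorded absence of change, so dI/dC does not describe the error. The absence of control testing is itself an inference, since the creatinine sentences name no arm.

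**The case for a change.** The strongest case for a change is that an analysis plan exists to settle such matters before the data are seen, and nothing in this one bars a by-arm or pooled rate. The unlisted secondary regressions leave room for one. The error would run in an awkward direction, making the better-monitored arm look worse, and a sentence of wording would prevent it. The routes by which control events surface are passive, and the documents do not show that the follow-up surveys ask about STI diagnoses, so detection would stay unequal.

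The facts behind this stand: the schedule is asymmetric, the sentence is thin, and a naive by-arm comparison of bacterial STI would be misleading. What does not stand is the step from a thin sentence to a biased analysis. The asymmetry is stated plainly in several sections, and the natural reading of a safety measure here is a description of the arm to which the study prescribes and in which it tests. Nothing suggests that the safety committee would be unaware of the schedule; labelling its tables by source of event would be good practice, not the correction of an error.

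**Conclusion.** No change to the plan is needed. Followed as written, it produces no wrong result: it states no comparison and no pooled rate for these measures, and the missing detail is of a kind that analysts fill sensibly. They would report HIV and STI rates from scheduled testing descriptively, over the participants tested, list control events that came to light by other routes separately, and keep known seroconversions from either arm in the 10.3.2 description.

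The figures above (an apparent ratio of 1.33 to 4.0, and false rejection from under 1% to 91%) rest on assumed risks, assumed detection shares and a test that nobody has planned. They show why a by-arm STI comparison would be unwise, not that one is intended. The primary outcome, its power, the interim bounds and the modelled cost-effectiveness analysis are untouched.

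The sentences that name no arm (HIV in 6.2.2, creatinine in 5.5 and 5.5.3) need to be read together and reconciled with 5.5, 5.5.2 and 8.1. That is a matter of wording, and nothing here says which testing schedule is right. The conclusion would differ if a between-arm or pooled analysis of these measures were specified elsewhere.
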